4.1.2. Randomization and Blinding

Not applicable.

4.1.3. Duration of Subject Participation

The planned length of the trial is up to 42 ± 2 days (from Screening through trial completion) for each enrolled subject.

Screening period: Lasts a maximum of 28 days; starts with the full signature (subject and Investigator/delegate) of the ICF and ends with the subject's enrollment or screening failure.

Treatment period: Starts and ends with the administration of a single apaglutide dose.

Post-treatment observation period: Starts on Day 1, the day of dosing of apaglutide, and ends 14 ± 2 days after the dose of apaglutide. For the first 8 days, the subjects will remain at the CRU.

Safety follow-up period: Starts the day after the dose of apaglutide and ends 14 ± 2 days later with the EOT visit. Subjects with AEs related to the investigational medicinal product (IMP) will be followed up until resolution or until deemed unresolvable.

The subject is expected to participate in the trial for a duration of up to 14 ± 2 days.

The visit schedule and protocol-mandated procedures are performed according to the Schedule of Events ([Table 1](#)).

4.1.4. Subject Completion

The subject is classified as having completed the trial following the EOT visit.

4.1.5. End of Trial Definition

The end of the trial is defined as the last subject last visit.

The Sponsor may terminate the trial prematurely according to certain circumstances, for example:

- Ethical concerns
- Insufficient recruitment
- When the safety of the subjects is doubtful or at risk, respectively
- Alterations in accepted clinical practice that make the continuation of a clinical trial unwise
- Early evidence of harm of the experimental intervention

4.1.6. Screen Failures

Specific data (demographics, informed consent date, medical history, reason for screen failure and AEs) will be collected during the Screening assessments and entered into the electronic Case Report Form (eCRF) for all subjects that are screen failures.

If after Screening the subject still does not meet all inclusion criteria, or meets one or more of the exclusion criteria, the subject is considered a screening failure. The reason will be entered into the eCRF. If only one laboratory result does not reach the limit for inclusion, one re-testing is allowed within the screening period.

Subjects that failed Screening may be re-screened once at a later stage if the reason for screening failure has changed over time (e.g., out of range laboratory values have resolved). Re-screening must occur at least 1 week from time of screen failure and requires re-consenting and Sponsor approval. Subjects who are re-screened will receive a new subject number.

4.1.7. Trial Safety Supervision

An external expert hepatologist has been appointed to provide ongoing assessments and advice regarding serious hepatic adverse events of special interest (AESI) that require further evaluation during the trial.

4.2. Treatment Alteration and Interruption

Not applicable.

4.3. Stopping Rules

4.3.1. Trial Stopping Rules

The trial can be stopped after completion of Part 1 according to the criterion described in [Section 4.1.1](#).

If the Investigator, the Sponsor, or the Safety Medical Monitor (who reviews medical information and safety data, and consults with the site on eligibility criteria) becomes aware of conditions or events that suggest a possible hazard to subjects if the trial continues, the trial may be terminated after appropriate consultation between the relevant parties. The trial may also be terminated early at the Sponsor's discretion in the absence of such a finding.

Conditions that may warrant termination include, but are not limited to:

- The discovery of an unexpected, significant or unacceptable risk to the subjects enrolled in the trial
- Failure of the site to enroll subjects at an acceptable rate
- Enrollment and further dosing of new subjects will be interrupted if two or more subjects experience AESIs such as fluid overload, persistent abdominal pain, gall bladder, biliary and pancreatic disease of Grade 3 and above, according to the National Cancer Institute – Common Terminology Criteria for Adverse Events (NCI-CTCAE), version 5 [\[CTCAE, 2017\]](#) of moderate intensity and/or if one or more subjects experience a Grade 4 event (unless clearly not attributable to the trial drug)

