11.1.1. Intensity of Adverse Events

The intensity of AEs is graded using the NCI-CTCAE scale ([CTCAE, 2017](#)).

Where the event is not specified in the scale, then the following definitions should be used to determine mild, moderate and severe events:

- Grade 1 (Mild): the event may be noticeable to the subject. It does not usually influence daily activities, and normally does not require intervention
- Grade 2 (Moderate): the event may make the subject uncomfortable. Performance of daily activities may be influenced, and intervention may be needed
- Grade 3 (Severe): the event may cause noticeable discomfort and usually interferes with daily activities. The subject may not be able to continue in the trial, and treatment or intervention is usually needed
- Grade 4 (Life-threatening): the subject was at risk of death; this does not apply if the subject might have been at risk of death if the event was more severe
- Grade 5 (Fatal)

A mild, moderate, or severe (Grades 1–3) AE may or may not be serious. Life-threatening and fatal (Grades 4 and 5) are always serious. These terms are used to describe the intensity of a specific event. Medical judgment will be used on a case-by-case basis.

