11.2.1. Injection Site Reactions

Subjects will be monitored for ISRs for at least 1 hour after IMP administration given at site, during a trial visit at the site, or longer (i.e., until the reaction stops or the subject leaves the site), as necessary. The individual symptoms of the ISR will be reported as AEs throughout the entire duration of the trial.

Data on local tolerability will be collected as an AESI. The following characteristics of ISRs will be documented:

- Pain
- Erythema
- Induration

This document is proprietary to VectivBio and for restricted circulation and access only.

- Pruritus
- Bruising

Severity (as described in **Table 4**) and duration of these features of the ISR will be collected by the site by direct observation when the IMP is administered on site.

Table 4 Grading of Severity is based on National Cancer Institute—Common Terminology Criteria for Adverse Events 5.0 in line with other Adverse Events in this trial

Pain	
Grade 1	Mild Pain
Grade 2	Moderate pain; limiting instrumental ADL
Grade 3	Severe Pain; limiting self-care ADL
Pruritus	
Grade 1	Mild, localized reaction with only topical intervention
Grade 2	Moderate with noticeable skin change from scratching (e.g., excoriation). Oral therapy indicated
Grade 3	Widespread and resulting in treatment interruption
Induration	
Grade 1	Mild induration with skin able to slide and pinch up
Grade 2	Unable to pinch up skin but still slides
Grade 3	Severe, unable to slide or pinch, potentially limiting ADL and consideration of treatment interruption
Erythema	
Grade 1	Mild, <2.5 cm
Grade 2	Moderate, 2.5–5 cm
Grade 3	>5 cm
Bruising	
Grade 1	Mild, <2.5 cm
Grade 2	Moderate, 2.5–5 cm
Grade 3	>5 cm

ADL=activity of daily living

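### The two-subject AESI dosing halt in Protocol 4.3.1 carries two severity thresholds, Grade 3 and above and moderate, so it is unsettled whether Grade 2 AESIs count

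*Protocol*

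**What the plan says.** Protocol 4.3.1 lists conditions that may lead to termination. One bullet says that enrolment and dosing of new subjects will be interrupted when two or more subjects have qualifying AESIs. The examples begin "AESIs such as fluid overload, persistent abdominal pain, gall bladder" and run on to "biliary and pancreatic disease of Grade 3 and above, according to the National Cancer Institute", citing CTCAE version 5. After that citation the clause continues "of moderate intensity and/or if one or more subjects experience a Grade 4 event", and it closes with a bracketed exception for events clearly not due to the drug.

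Section 11.1.1 ties the words to the numbers: "Grade 2 (Moderate): the event may make the subject uncomfortable" and "Grade 3 (Severe): the event may cause noticeable discomfort and usually interferes with daily activities". It repeats the mapping in general form: "A mild, moderate, or severe (Grades 1–3) AE may or may not be serious". Table 4 in Section 11.2.1 follows it for injection site reactions, where Grade 2 pain is "Moderate pain; limiting instrumental ADL".

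Section 4.3.1 also has a general clause for when the investigator, the sponsor or the Safety Medical Monitor "becomes aware of conditions or events that suggest a possible hazard to subjects if the trial continues". In that case the trial may be terminated after consultation.

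**The concern.** An event cannot be both Grade 3 or above and moderate in the protocol's own terms. Two subjects with Grade 2 AESIs, or one with Grade 2 and one with Grade 3, would therefore trigger the halt on one reading and not on the other. The investigator and the sponsor could disagree in good faith while subjects are still waiting to be dosed. Section 1.2.1 has the subjects with moderate hepatic impairment recruited before the controls, so the question can arise with most of the trial still to run.

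This bullet is the only safety halt in the protocol with a stated number of subjects. At stake is whether a Grade 2 pair counts under that rule or is left to judgement under the general hazard clause.

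**Working it through.** The protocol gives no operating characteristic for the halt, so there is no figure to reproduce. The check is a comparison of text, followed by an illustration on assumed rates.

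**Step 1: the thresholds side by side**

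| Place | Term | Grade |
|---|---|---|
| 4.3.1, before the CTCAE citation | Grade 3 and above | 3 or more |
| 4.3.1, after the citation | moderate intensity | 2, by 11.1.1 and Table 4 |
| 4.3.1, second limb | Grade 4 event, one subject | 4 |

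The first two rows qualify the same two-subject limb and exclude each other.

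**Step 2: does other text settle it?** Section 4.3.2 has no individual stopping rules. Section 11.2 sets no halting grade. Section 12.2.1 is marked not applicable, but it sits under sample size and says little about a clinical halt. The SAP has no dosing halt for adverse events, and would not normally hold one. Nothing reconciles the two terms.

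**Step 3: where the workable readings differ.** Take the worst AESI grade in each of two subjects, both below Grade 4. The unordered pairs are (1,1), (1,2), (1,3), (2,2), (2,3) and (3,3).

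- Grade 3 and above: halts on (3,3), 1 of 6.
- Grade 2 and above: halts on (2,2), (2,3) and (3,3), 3 of 6.
- They differ on (2,2) and (2,3): 3 − 1 = 2 of 6.

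This shows where the readings differ. The pairs are not equally likely, so 2 of 6 is not a probability. Both readings halt on two Grade 3 AESIs.

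**Step 4: illustration only.** The documents give no AESI rates by grade. Assume independent subjects, a worst AESI of Grade 3 in p3 = 1% of subjects, and of Grade 2 in p2 = 2%, 5% or 10%. The Grade 4 limb and the exception for events not due to the drug are ignored. With

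P(at least 2 of n) = 1 − (1 − p)^n − n·p·(1 − p)^(n−1),

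the chance that the readings give different decisions is P at p = p3 + p2 minus P at p = p3.

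| p2 | n = 8 | n = 16 (Part 1) |
|---|---|---|
| 2% | 0.0223 − 0.0027 = 2.0% | 7.1% |
| 5% | 0.0792 − 0.0027 = 7.6% | 0.2489 − 0.0109 = 23.8% |
| 10% | 0.2171 − 0.0027 = 21.4% | 52.8% |

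Percentages come from unrounded values. The spread reflects the assumed rates and the choice of n. None of these figures is a property of the trial.

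**The case against.** **Intent is fairly clear.** A numeric grade on a named scale and version is a deliberate threshold, while the moderate qualifier trails after the citation and looks like leftover text. The Grade 2 reading also gives an odd result. Injection site reactions are AESIs, so two subjects with erythema of 2.5–5 cm (Grade 2 in Table 4) could halt dosing. This stands, and it makes Grade 3 and above the likelier intent. It does not remove the contradiction from the text.

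**The mapping of moderate to Grade 2 is narrower than it looks.** The definitions in 11.1.1 are for events that CTCAE does not specify, and Table 4 covers injection site reactions only. That is correct, but the general sentence on Grades 1–3 in 11.1.1 has no such limit, and the protocol offers no other mapping.

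**Grade 3 might attach only to gall bladder, biliary and pancreatic disease, and moderate to the rest.** Nothing in the sentence marks such a split, and the status of Grade 2 events would still not be stated clearly.

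**The halt is not purely automatic.** The bullet says dosing will be interrupted, but it sits under a heading about conditions that may warrant termination. The exception for events clearly not due to the drug may also apply to both limbs. This stands: judgement is already part of the rule, and the reach of the exception needs stating too.

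**Impact is small.** Section 1.3.1 says most GLP-2 class effects are unlikely after one dose. Section 1.3 reports single doses up to 56.9 mg tolerated in healthy volunteers, though not in hepatic impairment. This stands, with one reservation: 1.3.1 also lists injection site erythema among the most frequent events.

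A reader might go further and infer that the contradictory limb can never be met, so that the trial has no working halt. The documents do not support that. Two Grade 3 AESIs halt dosing on either workable reading, and the Grade 4 limb and the hazard clause stand on their own.

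**Conclusion.** The two-subject limb of 4.3.1 is wrong as written. It contradicts itself on severity and leaves open whether Grade 2 AESIs count. Grade 3 and above is the likelier intent. The ambiguity is confined to pairs that include a Grade 2 event and no event above Grade 3. The PK analysis is untouched, and the practical impact is probably small after a single 5 mg dose. The conclusion rests on the protocol's own mapping of moderate to Grade 2 and not on the illustrative rates.

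Two neighbouring points should not be read as part of the error.

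- **Reporting time.** Section 11.2 allows up to 2 weeks to communicate an AESI, against 24 hours for a serious event in 11.3. A reader might infer that the halt cannot work in time. The 2 weeks is a maximum, and 11.2 itself says rapid communication can be appropriate. Section 4.1.3 keeps subjects in the unit for the first 8 days. The investigator and the Safety Medical Monitor can both act under 4.3.1. Faster notice is a reasonable suggestion.
- **The AESI list.** Section 4.3.1 treats persistent abdominal pain as an AESI, but 11.2.1 to 11.2.6 do not list it. This is a matter of alignment.

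**What to change.** In Protocol 4.3.1, delete the moderate qualifier so that the two-subject limb reads Grade 3 and above on CTCAE version 5. If the sponsor meant the more protective rule, replace the threshold with Grade 2 and above. The choice is the sponsor's, but only one threshold should remain. In the same edit, state whether the exception for events clearly not due to the drug applies to the two-subject limb as well as to the Grade 4 limb.

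Optional: add persistent abdominal pain to the AESI list in 11.2, and ask sites to notify the sponsor within 24 hours of any event that counts towards the halt, serious or not.

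The cost is a wording change, with no added subjects, visits or samples. The downside of the deletion is that repeated Grade 2 AESIs would be handled only under the discretionary hazard clause. The downside of Grade 2 and above is that minor events, such as two moderate injection site reactions, could interrupt dosing.

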11.3. Serious Adverse Events

An SAE is any untoward medical occurrence that at any dose:

- Results in death
- Is life-threatening
- Requires inpatient hospitalization or prolongation of existing hospitalization
- Results in persistent or significant disability/incapacity
- Is a congenital anomaly/birth defect

Medical and scientific judgement will be exercised in deciding whether reporting is appropriate in other situations, such as important medical events or reactions that may not reach the above definition but may jeopardize the subject or may require medical or surgical intervention to prevent one of the other outcomes listed in the above definition. These will also be considered serious. Examples of such events are invasive or malignant cancers, intensive treatment in an accident and emergency department or at home for allergic bronchospasm, blood dyscrasias or convulsions that do not result in hospitalization, or development of drug dependency or drug abuse.

All SAEs must be reported immediately and within a maximum of 24 hours to the CRO and/or Sponsor of the trial by using a paper version of the SAE form, which can

be emailed to [contact] or faxed. Local fax-numbers will be made available in the Investigator Site File, if email does not work.

The CRO/Sponsor will re-evaluate the SAE and queries will be raised in the eCRF or by email/fax and returned to the site, requesting clarification or follow-up information if needed. After the initial SAE report, the Investigator is required, proactively, to provide further information regarding the subject's condition. All follow-up information obtained after initially reporting the SAE, updates on the SAE, and any other new SAEs must be entered into the CRF as soon as possible as applicable, i.e., within 24 hours after new information becomes available. The Investigator must update the information as applicable in the eCRF and/or send an email to: [contact]. Local fax-numbers will be made available in the Investigator Site File, if email does not work. Serious AEs resulting in death or which are life-threatening will be reported to the Ethics Committee within 7 days.

The minimum data required for a report is:

- Subject ID
- Trial code/protocol number
- Description of SAE or SAE term
- Assessment of causality relationship to IMP
- Name and contact details of person reporting the event

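### The one-subject interruption trigger in Protocol 4.3.1 names Grade 4 only, so a single death recorded only as Grade 5 does not meet it as written

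*Protocol*

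**What the plan says.** The last bullet of Protocol section 4.3.1 (Trial Stopping Rules) contains two triggers joined by and/or.

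- **Two-subject trigger.** "Enrollment and further dosing of new subjects will be interrupted if two or more subjects experience AESIs", with examples that end in "gall bladder, biliary and pancreatic disease of Grade 3 and above".
- **One-subject trigger.** The same interruption follows "if one or more subjects experience a Grade 4 event (unless clearly not attributable to the trial drug").

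Section 11.1.1 grades intensity on the NCI-CTCAE scale and gives fallback definitions for events not specified there. These include "Grade 4 (Life-threatening): the subject was at risk of death", with Grade 5 (fatal) listed as a separate category. The same section says: "Life-threatening and fatal (Grades 4 and 5) are always serious".

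Other clauses bear on a death:

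- The hazard clause in 4.3.1 says "the trial may be terminated after appropriate consultation between the relevant parties".
- Section 4.1.5 says "The Sponsor may terminate the trial prematurely according to certain circumstances", and its examples include doubtful subject safety and early evidence of harm.
- Section 11.3 says "All SAEs must be reported immediately and within a maximum of 24 hours to the CRO and/or Sponsor of the trial". It also requires fatal or life-threatening events to go to the ethics committee within 7 days.

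**The concern.** The two triggers sit in one sentence but set their thresholds differently. The two-subject trigger runs upward from Grade 3. The one-subject trigger names one grade and stops there. Because the protocol treats death as a grade of its own, the one-subject trigger read literally covers a life-threatening event and omits a fatal one. A safety threshold should not become less demanding as severity rises.

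At stake is whether dosing of new subjects must pause after a first death that is not clearly unrelated to the drug, or whether the pause depends on a case-by-case decision. This is the only one-subject trigger in the protocol worded as a requirement to interrupt.

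**Working it through.** The rule states no error rate or power, so the check is textual: apply both triggers literally to each grade, then look for any other clause that would require a halt.

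**Inputs.** The triggers are those of section 4.3.1. The grades are those of section 11.1.1. The case is one subject with one event that is not clearly unattributable to the drug, and no second qualifying subject.

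| Highest grade recorded | One-subject trigger met | Two-subject trigger met | Interruption required as written | Interruption required with Grade 4 or higher |
|---|---|---|---|---|
| 1, 2 or 3 | No | No (one subject only) | No | No |
| 4 | Yes | No | Yes | Yes |
| 5, same event earlier recorded as Grade 4 | Yes | No | Yes | Yes |
| 5 only | No | No | **No** | **Yes** |

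Only the last row changes under the correction. Two subjects with fatal AESIs already meet the two-subject trigger, because its threshold is open-ended. A single Grade 5 AESI supplies one of the two subjects needed there. A fatal event that is not an AESI supplies none.

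**Other clauses that might require a halt.**

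- 4.3.1 hazard clause: permits termination after consultation.
- 4.1.5: permits the Sponsor to terminate.
- 11.3: sets reporting duties, with no consequence for dosing.
- 4.3.2: no individual stopping rules, because the trial is single-dose.
- 4.1.7: the external hepatologist assesses and advises on serious hepatic AESIs; no power to halt is stated.
- 12.2.1 and the SAP: no safety halt rule. Neither is where such a rule would have to sit, so this shows only that the gap is not filled there.

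None of these requires interruption after one death.

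**Can a Grade 5-only record arise?** Yes. Cohort 1 has Child-Pugh B cirrhosis, and some subjects may leave the unit on Day 8 and return on Day 11 and Day 14. A sudden death between visits could be recorded as fatal with no earlier Grade 4 entry. This shows the route is open; it says nothing about how likely it is.

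**The case against.** The strongest reply is that the trigger is plainly meant as a floor. Someone who dies of an event was at risk of death from it, section 11.1.1 groups Grades 4 and 5 as always serious, and a rule that pauses for a near-death but not for a death defeats its own purpose. The bullet also belongs to a non-exhaustive list of conditions that may warrant termination, so the contrast between mandatory and discretionary clauses is softer than it first looks. Even the Grade 4 trigger carries a judgement about attribution. A death that may be drug-related would engage the hazard clause at once, and the Sponsor would hear of it within 24 hours.

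Most of this stands as an argument about consequences. The intent is hardly in doubt, and the Sponsor would very likely stop. It does not remove the omission. Where section 11.1.1 means both grades it names both, and section 4.3.1 names one. The list heading speaks of termination, whereas the bullet prescribes a different action, interruption, in mandatory terms. The purpose of such a trigger is to avoid relying on discretion or inferred intent.

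**Conclusion.** The point holds as a minor drafting error. Read exactly, the one-subject trigger leaves out one of five grades, and that grade is death. The affected case is narrow: a single death, recorded only as Grade 5, and not clearly unattributable to the drug.

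The practical likelihood of harm is low. Section 5.2 plans about 16 to 32 subjects, each given one 5 mg dose, and section 1.1.3 reports single doses up to 56.9 mg as well tolerated. Pharmacokinetic endpoints, the Part 2 decision and the analysis are unaffected.

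The conclusion rests on two readings: that a Grade 4 event means that grade alone, as the separate listing in section 11.1.1 supports, and that the bullet's own mandatory verb governs interruption despite the softer list heading. If the whole list were treated as illustrative, naming Grade 4 without Grade 5 would still be a mistake, with less effect.

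**What to change.** In the one-subject trigger of section 4.3.1, replace *a Grade 4 event* with *an event of Grade 4 or higher*, and keep the attribution exception unchanged.

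The change adds the two words *or higher* and alters no procedure, sample size or analysis. It does alter a safety threshold, so it is hard to class as purely administrative. Under section 13.2.1 it would need prior written ethics committee approval, and it can reasonably be bundled with the next amendment.

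The same bullet should be tidied at that time for a separate inconsistency: the two-subject trigger combines Grade 3 and above with moderate intensity, which section 11.1.1 defines as Grade 2. The correction proposed here does not resolve that.
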